## a. Brief Summary

We plan to use functional magnetic resonance imaging (fMRI) methods to assess brain changes following transcranial magnetic stimulation (rTMS), in 30 healthy participants. An additional 30 healthy controls will undergo an MRI scan, without use of rTMS or TBS. We will offer these 30 healthy controls an optional component involving 2 sessions of 3-10min of TBS, 1 session on the Magventure TMS device and 1 session on the Nextstim TMS device, in order to compare participant preference between the 2 TMS systems.

For the 30 healthy participants in the MRI+rTMS group, we will assess MRI scans following either/both standard rTMS or TBS (theta-burst stimulation- a novel form of transcranial magnetic stimulation, in participants. We will measure the effects of TMS applied to the motor cortex, a system that when stimulated produces a readily observable behavioral response (e.g., movement of a given body regions). We will also measure the effects of TMS applied to the dorsolateral prefrontal cortex, a target recognized for its anti-depressant effects.

Our goal is to determine how brain activity and blood flow during tasks and at rest change following the applications of TMS to the motor cortex and/or dorsolateral prefrontal cortex.

This study will provide an understanding of the functional brain and behavioral changes that occur following TMS.

---

## b. Objectives

Please note TMS/TBS are used interchangeably in this protocol as they refer to different settings on the same device, a transcranial magnetic stimulation device, and both types of settings will be used for this study.

This study proposes to: 1 - determine the heart rate changes that are seen with TMS stimulation. 2- determine the optimal burst frequency for TMS, 3-determine the optimal intersession interval for TMS, 4- compare the results of #1 and #2 in the same subjects, 5- determine the effect of TMS/TBS on the resting state functional connectivity. 6- in healthy participants, assess the regulation of neuroplasticity by affective state.

Aim 1: To determine the heart rate changes seen with TMS/TBS.

Hypothesis 1: Heart rate changes will be observed following stimulation.

Aim 2: To determine the optimal burst frequency.

Hypothesis 2: For cTBS, the optimal frequency will be 30Hz bursts at 6Hz while iTBS will be the traditional 50Hz bursts at 5Hz.

Aim 3: To determine the optimal intersession interval for spaced TBS.

Hypothesis 3: For cTBS, the optimal ISI will be 15 min while with iTBS the optimal ISI will be 30 min.

Aim 4: To determine the effect of spaced TBS on the resting state functional connectivity.

Hypothesis 4: Optimized spaced iTBS and cTBS will produce changes in the resting state functional connectivity between pre-motor and motor cortex. Those who have less fc change from iTBS will experience maximal cTBS change in fc (correlated with change in MEP) and vice versa.

Aim 5: To determine the effect of TMS/TBS on the resting state functional connectivity.

Aim 6: To assess the regulation of neuroplasticity by affective state in healthy control participants.

Hypothesis 6: Changes in amplitude and frequency band power of ERP responses to emotional faces following iTBS and cTBS will be differentially affected by different induced affective states. Changes in MEP amplitude following iTBS and cTBS will be differentially affected by different induced affective states.

This study has broad implications ranging from advancing our understanding of the basic mechanisms of TBS on brain function, cerebral blood flow, and pain perception and therapeutic implications that could impact classical rTMS treatment schedules based on the duration of effects of spaced TBS.

---

**c. Rationale for Research in Humans**

---

We are investigating the neural underpinnings and behavioral effects of brain stimulation in humans. As such, only human subjects can be used for this project.

---

**2. STUDY PROCEDURES**

---

**a. Procedures**

---

The study will consist of 4 experiments.

**PARTICIPANTS**

We will recruit 60 healthy controls for this study 30 participants in MRI+rTMS/TBS group and 30 participants in MRI only group. Participants will be 18-80 year-old right handed male and female with no history of psychiatric or neurological diagnoses and no current use of psychoactive medications. They will be recruited to participate in this study, all of whom will be blinded to the purpose of the study. All subjects will be screened for any contraindications to TMS and will give their informed written consent prior to participation.

#### HEALTHY CONTROLS: MRI ONLY GROUP

30 healthy controls will undergo an MRI scan, without use of rTMS or TBS. We will offer these 30 healthy controls an optional component involving 2 sessions of 3- 10min of TBS, 1 session on the Magventure TMS device and 1 session on the Nextstim TMS device, in order to compare participant preference between the 2 TMS systems.

#### EXPERIMENT 1: Heart rate changes

The first experiment will determine what heart rate changes are seen following TMS/TBS stimulation. Please note some participants will only be included in experiment 1, availability and scheduling permitting. Subjects will attend 2 sessions where they will receive TMS/iTBS at 70 -100 of active or resting MT, as determined by the investigator. They will receive either active or sham during a session, and the sessions will be in a randomly assigned order.

Stimulation may be applied to the vertex, Beam F3 location, or location determined by neuronavigation. These are all standard locations for stimulation. Various heart rate measurements and cortisol and/or other lab tests will be collected before and after stimulation. fMRI will be completed before and after stimulation. Various questionnaires (e.g. regarding mood will be collected before/after stimulation). Tasks designed to induce mild mental stress (e.g. mental math or similar) will be used during the experiment to create equivalent baseline conditions for all subjects.

#### EXPERIMENT 2: Optimal Burst Frequency

This next experiment will determine the optimal burst frequency for TBS, comparing iTBS30, iTBS50, cTBS30, and cTBS50 within the same individual. This experiment is an important stepping stone for the overall study, as it will determine how responses to cTBS and iTBS are linked. Subjects will attend four sessions no <4 days apart, receiving the cTBS50, cTBS30, iTBS50, and iTBS30 applied at 80 of RMT. The order in which they will receive each paradigm will be randomized between subjects. In all sessions, MEP recruitment curves will be recorded at baseline, as well as at 0, 20, 40, 60, 90, and 120 min following TBS applications. During the session, the subjects will watch a muted video so that they stay alert during the whole experiment.

Each subject will have 4 visits.

1. MEP----iTBS50----MEP
2. MEP----iTBS30----MEP

3. MEP----cTBS50---MEP
4. MEP----cTBS30---MEP

#### Stimulation and Recording

Subjects will be seated in a comfortable chair for all procedures. Single-pulse TMS will be used to evoke MEPs from the right first dorsal interosseous FDI muscle target muscle. Electromyographic recordings will be made from the right FDI and abductor pollicis brevis (APB), which serves as a control muscle, using two Ag–AgCl surface electrodes arranged in a belly-tendon montage. Signals will be sampled at a rate of 5 kHz, amplified 1000 and filtered 20–1000 Hz before we store on a computer for offline analysis. Single-pulse TMS with monophasic waveform will be applied using a Magventure Magpro X100 magnetic stimulator Magventure, Farum, Denmark connected to a figure-of-eight magnetic coil. The optimal scalp site for evoking MEPs in the right FDI will be identified from M1 with the help of neuronavigation. The coil direction will be kept perpendicular to the nearest sulcus.

The mapping of the optimal location will be done with a supra threshold stimulation intensity evoking MEPs of around 1mV. After finding the optimal location, the coil will be rotated slightly in the tangential plane to check whether the induced electric field is optimal if not, the coil direction will be adjusted. At the optimal location, the rMT will be calculated with Motor threshold hunting paradigm, i.e. PEST. Thereafter, a baseline recruitment curve will be done 90 rMT-150 rMT, 10 pulses/intensity, interstimulus interval 5s and a cortical silent period threshold will be calculated with PEST.

#### rTMS Stimulation

rTMS will be applied using a Magventure Magpro. The rMT at the optimal cortical FDI representation will be calculated with the PEST. The intensity of TBS application will be 70-100 active or resting MT, as determined by investigator.

#### Theta-Burst Stimulation

TBS will be applied with a biphasic waveform using a Magventure Magpro Magventure, Farum, Denmark. The rMT at the optimal cortical FDI representation will be calculated with the PEST. The intensity of TBS application will be 80 of rMT.

#### TBS Paradigms

iTBS and cTBS will be applied with biphasic waveform using a Magventure Magpro Magventure, Farum, Denmark. Two cTBS and two iTBS paradigms with varying pulse configurations will be employed in this study. cTBS50 consists of a total of 600 stimuli applied in bursts of 3 stimuli at 20 ms intervals 50 Hz, with bursts repeated at 200ms intervals 5Hz. In the cTBS30 paradigm, bursts consisted of 3 stimuli applied at intervals of 33.3 ms 30 Hz, with bursts repeated at 167 ms intervals 6 Hz. As with the cTBS50 paradigm, cTBS30 will consist of a total of 600 stimuli. iTBS50, consists of a total of 600 stimuli applied in bursts of 3 stimuli at 20 ms intervals 50 Hz, with bursts repeated at 200ms intervals 5Hz and an 8 second intertrain interval between triplet. iTBS30 consists of bursts consisted of 3 stimuli applied at intervals of 33.3 ms 30 Hz, with bursts repeated at 167 ms intervals 6 Hz for three bursts then a 8 second intertrain interval. As with the iTBS50 paradigm, iTBS30 will consist of a total of 600 stimuli. The intensity of TBS

application will be set relative to resting motor threshold (RMT), measured using a biphasic pulse waveform with the rTMS coil. RMT will be defined as the minimum stimulus intensity sufficient to evoke MEPs in the right FDI at rest with peak-to-peak amplitudes of at least 50  $\mu$ V in five of 10 consecutive trials. After TBS, MEP recruitment curves and cortical silent period thresholds will be recorded at 0, 20, 40, 60, 90, and 120 min following TBS applications.

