### TBS Paradigms

iTBS and cTBS will be applied with biphasic waveform using a Magventure Magpro Magventure, Farum, Denmark. One of two cTBS and two iTBS paradigms with varying pulse configurations will be employed in this study. cTBS50 consists of a total of 600 stimuli applied in bursts of 3 stimuli at 20 ms intervals 50 Hz, with bursts repeated at 200ms intervals 5Hz.

In the cTBS30 paradigm, bursts consisted of 3 stimuli applied at intervals of 33.3 ms 30 Hz, with bursts repeated at 167 ms intervals 6 Hz.

As with the cTBS50 paradigm, cTBS30 consists of a total of 600 stimuli. iTBS50, consists of a total of 600 stimuli applied in bursts of 3 stimuli at 20 ms intervals 50 Hz, with bursts repeated at 200ms intervals 5Hz and an 8 second intertrain interval between triplets. iTBS30 consists of bursts consisted of 3 stimuli applied at intervals of 33.3 ms 30 Hz, with bursts repeated at 167 ms intervals 6 Hz for three bursts then an 8 second intertrain interval.

In Experiment 1, the optimal burst frequency for both cTBS and iTBS will be determined and that optimal cTBS and iTBS frequency will be utilized in this portion of the study.

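### Do the iTBS30 and iTBS50 pulse figures in Experiment 2 contradict their 600-stimulus totals, or make the two arms differ in more than burst frequency?

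*Protocol*

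**What the plan says.** The Protocol's Experiment 2 is designed for "comparing iTBS30, iTBS50, cTBS30, and cTBS50 within the same individual". It serves the objective worded as "Aim 2: To determine the optimal burst frequency", and the chosen frequency is used in the later experiments.

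The TBS Paradigms section under Experiment 2 defines the two intermittent paradigms:

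- **iTBS50:** "iTBS50, consists of a total of 600 stimuli applied in bursts of 3 stimuli at 20 ms intervals 50 Hz", then "with bursts repeated at 200ms intervals 5Hz and an 8 second intertrain interval between triplet". The number of bursts per train is not given.
- **iTBS30:** 3 stimuli per burst at 33.3 ms spacing, then "bursts repeated at 167 ms intervals 6 Hz for three bursts then a 8 second intertrain interval". The total follows: "As with the iTBS50 paradigm, iTBS30 will consist of a total of 600 stimuli".

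The TBS Paradigms sections under Experiments 3, 4 and 5 repeat the iTBS50 wording with the plural, "with bursts repeated at 200ms intervals 5Hz and an 8 second intertrain interval between triplets". They repeat the three-burst description of iTBS30 but do not restate its total. No section gives a number of trains or an application time for either intermittent paradigm. The only TBS session length in the document is in the Brief Summary and the section on the MRI-only group, for "an optional component involving 2 sessions of 3-10min of TBS". That belongs to a separate comparison of participant preference between two devices.

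**The concern.** Two things look wrong on a first reading.

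1. **The iTBS30 total.** Three bursts of three stimuli make 9 per train, and 9 does not divide 600. A total given as a fixed stimulation setting, and said to match iTBS50, then seems not to follow from the train description.
2. **The iTBS50 gap.** The sentence gives a 200 ms burst interval and an 8 s gap between triplets. The only group of three that it names is the 3-stimulus burst. If the gap falls after every burst, an iTBS50 application takes nearly three times as long as iTBS30.

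The second point has the larger consequence. Experiment 2 compares the two paradigms within the same people in order to choose a frequency. If they also differed in train structure and by some 17 min of application time, a difference in motor evoked potentials could not be credited to the 30 Hz/6 Hz versus 50 Hz/5 Hz setting, and the choice would carry into later experiments.

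**Working it through.** **Inputs** (Protocol, Experiment 2, TBS Paradigms): 3 stimuli per burst; 600 stimuli in total; stimulus spacing 20 ms (iTBS50) and 33.3 ms (iTBS30); burst interval 200 ms and 167 ms; gap 8 s; three bursts per train for iTBS30. The gap is first taken from the end of one train to the start of the next.

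**Step 1: the total.**
- Bursts needed: 600/3 = 200, a whole number.
- Trains of three bursts: 600/9 = 66.67.
- Full trains only: 66 × 9 = 594 (−1.0%) or 67 × 9 = 603 (+0.5%).
- With a short last train: 66 × 9 + 2 × 3 = 600 exactly.

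The stated 600 is therefore reachable with 66 full trains and one two-burst train. The text gives a repeating pattern and a total. It states neither a number of trains nor that every train is full, so stopping at 600 satisfies every figure given.

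**Step 2: iTBS30 as written.**
- Full train: 2 × 0.167 + 2 × 0.0333 = 0.4006 s.
- Last train: 0.167 + 2 × 0.0333 = 0.2336 s.
- Application: 66 × 0.4006 + 0.2336 + 66 × 8 = 554.7 s = 9.24 min.

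**Step 3: iTBS50, triplet read as three bursts.**
- Full train: 2 × 0.2 + 2 × 0.02 = 0.44 s.
- Last train: 0.2 + 2 × 0.02 = 0.24 s.
- Application: 66 × 0.44 + 0.24 + 66 × 8 = 557.3 s = 9.29 min.
- Difference from iTBS30: 557.3 − 554.7 = 2.6 s, or 2.6/554.7 = 0.5%. All of it comes from the burst spacing under comparison.

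**Step 4: iTBS50, triplet read as one burst.**
- Application: 200 × 0.04 + 199 × 8 = 1600 s = 26.7 min.
- Against iTBS30: 1600/554.7 = 2.9 times, or 26.7 − 9.24 = about 17.4 min longer.
- Consistency: consecutive bursts would start 8.04 s apart (0.04 + 8). No burst would repeat at 200 ms, the 5 Hz figure would describe nothing, and every train would be a single burst.

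**Step 5: sensitivity to how the gap is measured.** The text does not say whether the 8 s runs from end to start, follows a full burst period, or runs from onset to onset.

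| Reading | End to start | After a full burst period | Onset to onset |
|---|---|---|---|
| iTBS30 | 554.7 s | 561.2 s | 528.2 s |
| iTBS50, three bursts | 557.3 s | 567.8 s | 528.2 s |
| iTBS50, one burst | 1600.0 s | 1631.8 s | 1592.0 s |

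On the three-burst reading the two paradigms differ by 0 to 6.6 s (567.8 − 561.2), whichever convention is used.

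**Step 6: the continuous paradigms.** Their 600 stimuli are exactly 200 bursts with no train structure, so nothing arises there.

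**The case for a change.** The strongest case for acting is that stimulation settings belong in the protocol and cannot be left to a statistical analysis plan. The term *triplet* is undefined, the nearest group of three is the burst itself, and the one-burst reading is the one under which 600 divides evenly. The later sections repeat the wording, so it is not a fault in reading one page. Hypothesis 2 expects iTBS50 to be the better intermittent setting, so the less clearly described paradigm is the one expected to go forward. The 3 to 10 min session length concerns another component and cannot define iTBS50.

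Part of this stands. The description is incomplete in three places: the meaning of *triplet*, the bursts per train for iTBS50, and the short last train needed for exactly 600.

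The step from there to a flawed comparison does not stand. Even division by one-burst trains comes at the price of the 200 ms interval and the 5 Hz figure, both stated in the same sentence. The three-burst reading keeps both and agrees with the parallel iTBS30 sentence. It leaves only the last train undescribed, and any rounding there, to 594 or 603, would be the same in both arms if they are run alike. The session length of 3 to 10 min proves nothing, but it gives no support to 26.7 min. The missing iTBS30 total in the later sections is no defect, because Experiment 2 has already stated it.

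**Conclusion.** The concern does not hold as an arithmetic error or as a confounded comparison. Read so that all its figures can be true together, the text gives two intermittent paradigms with the same three-burst trains, the same 8 s gap and the same 600 stimuli. They last about 9.24 and 9.29 min, 2.6 s apart (0 to 6.6 s across gap conventions). The 26.7 min figure requires discarding an interval that the sentence states. The count discrepancy is zero with a two-burst last train and at most 1% without one.

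What is left is a gap in description that the staff who program the stimulator settle in practice. Writing it out would tidy the text but would not alter the design, the within-subject comparison or its analysis.

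This rests on two assumptions: that *triplet* means three bursts, as the 200 ms interval and the iTBS30 sentence indicate, and that both arms handle the last train alike. The programmed sequences are not in the document and could not be checked. No view is taken on which stimulation parameters are right.

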### EXPERIMENT 3: Optimal Intersession Interval

This experiment builds on previous understanding of the optimal intersession interval for spaced TBS which suggests that for cTBS, the optimal ISI is 15 minutes while with iTBS the optimal ISI is 30 minutes. We will utilize the burst frequency determined to be optimal from experiment 1. We will apply TBS over the left, dominant M1. TBS will be repeated two times separated by 15, 30, 45, or 60 min intersession interval. Subjects will attend eight sessions no <4 days apart, receiving the cTBSXX-15-cTBSXX, cTBSXX-30-cTBSXX, cTBSXX-45-cTBSXX, cTBSXX-60- cTBSXX, iTBSXX-15-iTBSXX, iTBSXX-30-iTBSXX, iTBSXX-45-iTBSXX, and iTBSXX-60-iTBSXX applied at 80 of RMT. The order in which they will receive each paradigm will be randomized between subjects. MEP recruitment curves and cortical silent period thresholds will be recorded at baseline, and at 0, 20, 40, 60, 90, and 120 min following the second TBS application.

Each subject will have 8 visits. 22 number of participants.

1. MEP----iTBSXX----15 min----iTBSXX----MEP
2. MEP----iTBSXX----30 min ----iTBSXX----MEP
3. MEP----iTBSXX----45 min ----iTBSXX----MEP
4. MEP----iTBSXX----60 min ----iTBSXX----MEP
5. MEP----cTBSXX----15 min ----cTBSXX----MEP
6. MEP----cTBSXX----30 min ----cTBSXX----MEP
7. MEP----cTBSXX----45 min ----cTBSXX----MEP
8. MEP----cTBSXX----60 min ----cTBSXX----MEP

XX=optimal burst frequency from experiment

Motor Evoked Potentials (MEPs)

Subjects will be seated in a comfortable chair for all procedures. Single-pulse TMS will be used to evoke MEPs from the right first dorsal interosseous (FDI) muscle.

Electromyographic recordings will be made from the right FDI using two Ag- AgCl surface electrodes arranged in a belly-tendon montage. Signals will be sampled at a rate of 5 kHz, amplified #1000 and filtered 20–1000 Hz before we store on a computer for offline analysis. Single-pulse TMS with monophasic waveform will be applied using a Magventure Magpro X100 magnetic stimulator Magventure, Farum, Denmark connected to a figure-of-eight magnetic coil external wing diameter, 90 mm. The coil will be held tangentially to the skull over the left M1, with the handle pointing 45° posterolaterally. The optimal scalp site for evoking MEPs in the right FDI will be identified and marked using a Watersoluble felt marker, and the intensity of stimulation will be adjusted to evoke baseline MEPs of approximately 1 mV amplitude measured peak-to peak.

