#### EXPERIMENT 4: Neuroimaging

This experiment will form the bulk of the study and involves determining the rs fc MRI changes seen with spaced TBS, as well as determining how these rs fc MRI changes correlate with iTBS/cTBS response. Functional connectivity between pre-motor and motor cortex will be assessed. MRIs will be done at the Center for Cognitive and Neurobiological Imaging at Stanford University, or at the Richard Lucas Center for Imaging. All scans will be governed by each respective imaging center's safety protocols.

Resting state functional MRI and MR spectroscopy may be performed. The experimental procedures TBS applications of the fMRI sessions will be timed equivalent to the time 0 post spaced theta-burst stimulation of the MEP sessions from Experiment 2. In addition to the MEP acquisition, resting-state fMRI time series will be acquired at baseline and after the second application of cTBS and iTBS. Before the baseline fMRI measurements, the "hotspot" and RMT will be assessed using the neuronavigation setup. Subjects will attend two sessions no <4 days apart, receiving the cTBSXXYY-cTBSXX, and iTBSXX-YY-iTBSXX applied at 80 of RMT. The order in which they will receive each paradigm will be randomized between subjects. The fMRI sessions will start with a baseline resting-state scan duration 10 min where subjects will be instructed to lie motionless in the scanner with open eyes fixating a red cross, which was presented on a screen visible through a mirror attached to the MR head coil. After completion of the resting-state MRI, subjects will be asked to perform an active motor task, which will serve as a functional localizer for determining coordinates of M1 and other motor related regions for subsequent analyses.

This "activity" condition will be acquired after the resting state scan. After completion of the baseline fMRI session, subjects will be transported from the scanner to the anteroom of the MR console again sitting in the MR wheelchair without moving their right arm.

After coregistration with the neuronavigation system, spaced TBS will be applied separated by YY min controlled by a stopwatch. After the TBS, there will be another resting-state fMRI. The time protocol in the fMRI sessions will be identical to the one used in the MEP sessions.

Each subject will have 2 visits.

1. MRI----iTBSXX---YY min----iTBSXX---MRI
2. MRI----cTBSXX---YY min ----cTBSXX---MRI

XX=optimal burst frequency from experiment 1  

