produces effects that are opposite to the intended effect. Spaced, patterned theta-burst is therefore required. sTBS was assessed in healthy controls with MEP change and it has been demonstrated that RMT70 produces 2 hours of suppression of the MEP which is affected by preceding hand activation. This approach has been assessed for saccade induction with non-linear increases in saccades. Recently, the technique has been applied to disease conditions such as hemispatial neglect and depression.

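### Experiments 2 and 3 schedule contraction of the target muscle before TBS and at every follow-up time, so the absolute duration of the resting-MEP effect cannot be separated from an activation effect

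*Protocol*

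**What the plan says.** All places are in the protocol.

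- **Experiment 2, Stimulation and Recording.** The baseline sequence ends with two measures. First "a baseline recruitment curve will be done 90 rMT-150 rMT, 10 pulses/intensity, interstimulus interval 5s", then "a cortical silent period threshold will be calculated with PEST". The right FDI is named as the target muscle.
- **Experiment 2, TBS Paradigms.** The follow-up plan reads: "MEP recruitment curves and cortical silent period thresholds will be recorded at 0, 20, 40, 60, 90, and 120 min following TBS applications". The resting motor threshold in the same section is defined with the FDI at rest.
- **Experiment 2, opening section.** The session schedule mentions one measure: "MEP recruitment curves will be recorded at baseline, as well as at 0, 20, 40, 60, 90, and 120 min". The silent period does not appear there.
- **Experiment 3.** Here the silent period is named at baseline too, alongside the MEP measure: "cortical silent period thresholds will be recorded at baseline, and at 0, 20, 40, 60, 90, and 120 min following the second TBS application".
- **Section 3a, Spaced Theta-Burst Stimulation.** Spaced TBS at the cited intensity "produces 2 hours of suppression of the MEP which is affected by preceding hand activation".
- **Section 2g.** The primary endpoint is how long the effect of a TBS application lasts. The measure is not named.
- **Section 1b.** No aim or hypothesis refers to the silent period.

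**The concern.** The silent period is an interruption of ongoing voluntary EMG. That is the definition of the measure: it cannot be obtained from a relaxed muscle. The schedule therefore asks for hand contraction before TBS and again around each resting-MEP reading, while the background section names preceding hand activation as something that alters the MEP effect of spaced TBS.

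Only Experiments 2 and 3 have a 0 to 120 min series after TBS, so they are the evident source for the duration endpoint. If contraction shifts resting MEPs or changes the effect that TBS induces, the reported duration mixes the TBS effect with a product of the measurement. Neither experiment has a sham or no-TBS session that would show what repeated contraction and time do alone; in the protocol, sham appears only in Experiment 1.

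**Working it through.** The plan gives no figure to reproduce. The check is a count of the schedule and a reading of its order.

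**Inputs.** One baseline search (Experiment 2, Stimulation and Recording; Experiment 3). Six post-TBS times: 0, 20, 40, 60, 90 and 120 min (same two experiments). Sessions per participant: 4 in Experiment 2, 8 in Experiment 3. Recruitment curve: 90 to 150 relative to rMT, 10 pulses per intensity, 5 s apart. The step between intensities is not given.

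**Silent period searches.**
- Per session: 1 + 6 = 7.
- Experiment 2, per participant: 7 × 4 = 28.
- Experiment 3, per participant: 7 × 8 = 56.

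**Searches already done when each resting curve starts**, if the curve comes first at each time, as listed:

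| Curve | Baseline | 0 | 20 | 40 | 60 | 90 | 120 min |
|---|---|---|---|---|---|---|---|
| Prior searches | 0 | 1 | 2 | 3 | 4 | 5 | 6 |

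The number of prior searches rises with time since TBS in every session. Time and cumulative contraction therefore move together, and no session without TBS exists to pull them apart. The protocol lists the curve before the silent period at the post-TBS times but does not fix that order. If the silent period came first, each post-TBS curve would follow one more search.

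**Room for rest between readings.** Curve length = intensities × 10 pulses × 5 s. The step size is my assumption:
- 10-point steps, 7 intensities: 7 × 10 × 5 = 350 s, about 5.8 min.
- 20-point steps, 4 intensities: 4 × 10 × 5 = 200 s, about 3.3 min.
- 5-point steps, 13 intensities: 13 × 10 × 5 = 650 s, about 10.8 min.

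With 10-point steps and the curve done first, about 20 − 5.8 = 14 min of each 20-min gap, and 30 − 5.8 = 24 min of each 30-min gap, remain for the silent period search and rest. Over the assumed range the 20-min gap leaves 20 − 10.8 = 9.2 to 20 − 3.3 = 16.7 min. So there is time to measure and then rest, but the protocol sets no rest period, no contraction level and no check of background EMG before a resting MEP.

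**Position before TBS.** In Experiment 2 the silent period search is the last baseline measure listed. In Experiment 3 it precedes the first TBS, so it lies at least 15, 30, 45 or 60 min before the second, depending on the interval under test.

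**The case against.** Several stronger readings are tempting, and the protocol does not support them.

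- **That contraction after TBS is documented to distort every later reading.** A reader might infer this from the background sentence. That sentence concerns activation that precedes spaced TBS and its effect on MEP suppression. It says nothing about contraction at 20 or 60 min after TBS. Experiment 2 uses single applications, and half of its conditions are iTBS. For the six later searches the problem is that the design cannot rule out an effect, not that the protocol documents one.
- **That the chosen burst frequency and interval are biased.** All sessions of an experiment carry the same silent period schedule, so a shift common to all conditions cancels in within-subject contrasts. Bias there needs activation to act differently by condition. The varying distance between the baseline search and the second TBS in Experiment 3 is one possible route, but nothing in the protocol shows that it operates.
- **That the search immediately precedes TBS.** The order is given but the gap is not. A biphasic resting threshold is also measured, at an unstated point.
- **That Experiment 4 shows the protocol guarding against hand activity.** Participants do travel to TBS "sitting in the MR wheelchair without moving their right arm", but the same section orders an active motor task before TBS. The imaging sessions are not a clean contrast.
- **That the Experiment 2 sections flatly contradict each other.** The opening schedule omits the silent period; it does not exclude it. It may be an incomplete summary.
- **That the endpoint is stated to be the resting MEP.** Section 2g names no measure, and a silent period time course could itself be read as duration.

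These points narrow the concern. They leave standing that the schedule brings in contraction of the muscle under study, that the protocol regards prior activation as relevant to the MEP effect, and that no control session exists.

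**Conclusion.** The point holds in limited form. Experiments 2 and 3 schedule 7 contraction-dependent measurements per session around a resting-MEP series, and without a sham or no-TBS session the absolute duration of the MEP effect cannot be separated from an activation effect. The size and direction of the bias cannot be derived from the protocol. The comparisons behind Aims 2 and 3 are largely protected and are affected only by an interaction of activation with condition.

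This rests on three assumptions: the silent period is recorded from the FDI, which is the stated target but is not named for this measure; the baseline steps run in the order listed; and duration will be read from resting MEPs. Rules for rejecting MEP trials may stand in a document not shown, but they would not settle the order and timing of the measurements.

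**What to change.** 1. Reconcile the Experiment 2 opening schedule with its Stimulation and Recording and TBS Paradigms sections, and state whether the silent period is measured there.
2. Where it is kept, do not leave it as the last step before TBS. Take it before the baseline recruitment curve, followed by a fixed rest period. The baseline and 0-min curves then each follow one search rather than none and one.
3. At each post-TBS time, always record the resting recruitment curve first and the silent period second.
4. Standardise the contraction level and the rest that follows it.
5. Confirm FDI relaxation on the EMG already attached before each resting MEP, and exclude trials with background activity.

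A simpler option is to drop the silent period, or to take it only after the 120-min curve. Since no aim or hypothesis uses it, that is acceptable but not required; the price is the silent period time course.

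Either route costs protocol wording. The first adds a fixed rest period before TBS and some lost MEP trials; the second shortens the sessions. Keeping the measure under steps 2 to 5 reduces the risk but does not remove it, because cumulative contraction still rises with time, so the report should say that duration was estimated under repeated contraction.
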